8.2.11 Early Termination Visit (if needed)

The following activities will be performed at the early termination visit on subjects who withdraw, or are withdrawn or terminated from this trial:

- Interim medical history, including an assessment for new medical conditions and symptoms suggestive of PIMMCs, will be obtained by interview of subjects and any changes since the previous clinic visit or contact will be noted.
- Memory aid information will be reviewed with subjects (if within 7 days after the last study vaccination).
- All concomitant medications will be recorded on the appropriate data collection form (if within 21 days after the last study vaccination). Receipt of any non-study influenza vaccine, including those that are experimental, what type (inactivated or live attenuated), what subtype (e.g., A/H3, A/H5, A/H9) and approximate date of vaccination will be recorded on the appropriate DCF, if known and not previously collected will be recorded if within 180 days after the second study vaccination.
- All AE/SAEs will be recorded on the appropriate data collection form. AEs will be limited to SAEs, MAAEs, including NOCMCs, and PIMMCs that have occurred since the previous clinic visit or contact will be solicited (if after 21 days after last study vaccination).
- Vital signs, including oral temperature, pulse, and blood pressure, may be obtained if indicated. Subjects must not eat or drink anything hot or cold, or smoke within 10 minutes prior to taking oral temperature.
- A targeted physical examination, including an assessment for signs suggestive of PIMMCs, may be performed, if indicated based on review of interim medical history, by a study clinician licensed to make medical diagnoses and listed on the Form FDA 1572 as the site principal investigator or sub-investigator.

- The study vaccination site will be examined (if within 7 days after the last study vaccination).
- Post-administration reactogenicity assessments will be performed (if within 7 days after the last study vaccination).
- Approximately 10 mL of venous blood will be collected for WBC, Hgb, PLT, ALT, T. Bili, Cr, and performed by the central (clinical) laboratory (if within 7 days after the last study vaccination).
- Approximately 10 mL of venous blood will be collected for serum antibody assays (if within 21 days after the last study vaccination).
- Approximately 10 mL of venous blood will be collected for future research (if within 21 days after the last study vaccination) from subjects who consent to collection of serum for future use, either by signing an informed consent form that includes collection of future use samples as a condition of study participation or by indicating that they opt in to sample collection for future use if the informed consent form allows the option to choose that option.

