3.2 Study Outcome Measures

3.2.1 Primary

Safety:

- Occurrence of study vaccine-related serious adverse events (SAEs) from the time of the first study vaccination through approximately 12 months after the last study vaccination.
- Occurrence of solicited injection site and systemic reactogenicity events from the time of each study vaccination through 7 days after each study vaccination.
- Occurrence of clinical safety laboratory adverse events from the time of each study vaccination through approximately 7 days after each study vaccination.

Immunogenicity:

• For HAI and Neut antibodies, percentage of subjects achieving seroconversion against the influenza 2017 H7N9 study vaccine strain (defined as either a pre-vaccination titer <1:10 and a post-vaccination titer ≥1:40 or a pre-vaccination titer ≥1:10 and a minimum

- four-fold rise in post-vaccination titer) at approximately 21 days after the second study vaccination (Study Day 43).
- For HAI and Neut antibodies, percentage of subjects achieving titer ≥1:40 against the influenza 2017 H7N9 study vaccine strain at approximately 21 days after the second study vaccination (Study Day 43).
- Geometric Mean Titers (GMTs) of serum HAI and Neut antibodies against the influenza 2017 H7N9 vaccine strain at approximately 21 days after the second study vaccination (Study Day 43).

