- Subjects will be provided with a memory aid and other study-related materials to record daily oral temperature, solicited injection site and systemic reactions, any unsolicited AEs, and concomitant medications. Subjects will be encouraged to take their oral temperature around the same time each day. Subjects must not eat or drink anything hot or cold, or smoke within 10 minutes prior to taking oral temperature. Subjects will be instructed on how to use their memory aid and how to measure and record AEs prior to discharge from the clinic. Subjects will be instructed to notify the study center if they develop any severe reactions after the second study vaccination. If the site principal investigator or appropriate sub-investigator deems the reaction severe enough, further instructions will be given to the subject on the proper course of action, including a return to the clinic for immediate evaluation if appropriate.

8.2.4 Visit 05, Day 25, Memory Aid Review, Phone Call (Window: Day 4±1 day post second study vaccination)

Study personnel will contact subjects by phone to solicit any AE/SAE, medical history, and concomitant medication information (including solicitation for receipt of any non-study influenza vaccines, including those that are experimental, what type (inactivated or live attenuated), what subtype (e.g., A/H3, A/H5, A/H9) and approximate date of vaccination will be recorded on the appropriate DCF, if known and not previously collected.) and review information on their memory aid. Based on the information, subjects may be asked to return to the clinic for evaluation. Note: For subjects who are discontinued from the receipt of the second study vaccination, AEs will be limited to SAEs, MAAEs, including NOCMCs, and PIMMCs.

8.2.5 Visit 06, Day 29, Clinic Visit (Window: Day 8+2 days post second study vaccination)

- Interim medical history, including an assessment for new medical conditions, stability of chronic diseases, and symptoms suggestive of PIMMCs, will be obtained by interview of subjects and any changes since the previous clinic visit or contact will be noted.
- Memory aid information will be reviewed with subjects.

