- All concomitant medications (including solicitation for receipt of any non-study influenza vaccines, including those that are experimental, what type (inactivated or live attenuated), what subtype (e.g., A/H3, A/H5, A/H9) and approximate date of vaccination will be recorded on the appropriate DCF, if known and not previously collected.) will be recorded on the appropriate data collection form.
- All AE/SAEs will be recorded on the appropriate data collection form. Note: for subjects who discontinued from the receipt of the second study vaccination, AEs will be limited to SAEs, MAAEs, including NOCMCs, and PIMMCs.
- A targeted physical examination, including an assessment for signs suggestive of PIMMCs, may be performed, if indicated based on review of interim medical history, by a study clinician licensed to make medical diagnoses and listed on the Form FDA 1572 as the site principal investigator or sub-investigator.
- The second study vaccination site will be examined.
- Approximately 10 mL of venous blood will be collected for safety labs WBC, Hgb, PLT, ALT, T. Bili, Cr, and performed by the central (clinical) laboratory.
- Approximately 10 mL of venous blood will be collected for serum antibody assays.
- Approximately 10 mL of venous blood will be collected for future research from subjects
 who consent to collection of serum for future use, either by signing an informed consent
 form that includes collection of future use samples as a condition of study participation or
 by indicating that they opt in to sample collection for future use if the informed consent
 form allows the option to choose that option.

8.2.6 Visit 07, Day 43, Clinic Visit (Window: Day 22+7 days post second study vaccination)

- Interim medical history, including an assessment for new medical conditions, stability of chronic diseases, and symptoms suggestive of PIMMCs, will be obtained by interview of subjects and any changes since the previous clinic visit or contact will be noted.
- All concomitant medications (including solicitation for receipt of any non-study influenza vaccines, including those that are experimental, what type (inactivated or live attenuated), what subtype (e.g., A/H3, A/H5, A/H9) and approximate date of vaccination will be recorded on the appropriate DCF, if known and not previously collected.) will be recorded on the appropriate data collection form.

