4.4.5. Selection and Timing of Dose for Each Subject

Each subject is to be randomly assigned to a study group which will define the A/H7N9 vaccine dose and receipt of adjuvant for both planned study vaccinations. The first vaccination takes place on the day of randomization, and the second vaccination takes place approximately 21 days after the first vaccination (protocol defined window of 21-28 days post first vaccination).

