6.3.3. Per Protocol Population

The per protocol (PP) population includes all subjects in the mITT subset with the following exclusions:

- Data from all available visits for subjects found to be ineligible at baseline due to eligibility criteria that would impact immune response.
- Data from all visits subsequent to major protocol deviations, such as:
 - o Second study vaccination not received,
 - o Second study vaccination received out of window,
 - Receipt of non-study licensed live vaccine within 30 days before or after each study vaccination,
 - Receipt of non-study licensed inactivated vaccine within 14 days before or after each study vaccination,
 - Receipt of immunosuppressive therapy (e.g., corticosteroids) within 30 days before or after each study vaccination.
- Data from any visit that occurs out of window by more than one day:
 - O Visit 3 data collected before 6 days or after 10 days post first study vaccination
 - o Visit 4 data collected before 20 days or after 29 days post first study vaccination.
 - o Visit 6 data collected before 6 days or after 10 days post second study vaccination.
 - o For subjects who did not receive the second study vaccination, visit 6 data collected before 27 days or after 31 days post first study vaccination.
 - o Visit 7 data collected before 20 days or after 29 days post second study vaccination.
 - o For subjects who did not receive the second study vaccination, visit 7 data collected before 41 days or after 50 days post first study vaccination.
 - Visit 10 data collected before 165 days or after 195 days post second study vaccination.
 - o For subjects who did not receive the second study vaccination, visit 10 data collected before 200 days or after 216 days post first study vaccination.

For analyses using the PP population, subjects will be grouped based on study vaccinations received.

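### Two blood-draw timing rules conflict with the visit windows: early-termination serum stops at day 21 while the Day 43 window runs to day 28, and protocol Table 2 gives Visit 06 a different window from the rest of the plan

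*Protocol*

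**What the plan says.** **Early termination.** Protocol 8.2.11 sets the antibody draw as follows: "Approximately 10 mL of venous blood will be collected for serum antibody assays (if within 21 days after the last study vaccination"). The early-termination columns of Appendix A and SAP Table 3 repeat this limit. Section 8.2.11 limits the diary in the same style: "Memory aid information will be reviewed with subjects (if within 7 days after the last study vaccination"). The early-termination safety labs also stop at 7 days.

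**Visit 07.** Protocol 8.2.6 gives "Clinic Visit (Window: Day 22+7 days post second study vaccination"). This visit feeds the three primary immunogenicity outcomes in Protocol 3.2.1, each set "at approximately 21 days after the second study vaccination (Study Day 43").

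**Visit 06.** Protocol 8.2.5 gives "Clinic Visit (Window: Day 8+2 days post second study vaccination"). Appendix A and SAP Table 2 agree with it. Protocol Table 2, the venipuncture table, gives D8±3d for the same visit.

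**Analysis.** SAP 6.3.3 removes from the per-protocol (PP) population "Visit 6 data collected before 6 days or after 10 days post second study vaccination", and Visit 7 data before day 20 or after day 29. The mITT definition in SAP 6.3.2 has no visit-window exclusion. Protocol 11.6.4 and SAP 6.5 plan no imputation.

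**The concern.** The protocol means to use serum from subjects who leave. Section 5.2.4 encourages them to attend the early-termination visit, and Section 7.2.2 has their available sera assayed. Yet the draw rule ends on the day the Day 43 window opens. A subject can be in clinic, inside the primary window, with no sample called for. Without imputation that Day 43 result is missing from both mITT and PP, and it comes from someone who is withdrawing, so it may not be missing at random.

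For Visit 06, a site that schedules blood draws from Table 2 could draw on day 4 or 5 and believe itself compliant. PP would drop the titer, while mITT would report it under the SAP Table 29 label of 7 days after vaccination 2. The post-dose-2 safety labs would also be drawn several days before the roughly 7-day point in the endpoint definition.

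**Working it through.** **Day count.** Protocol Table 2 marks the dose 2 day as D1, so days elapsed = study day − 1. Check against the SAP: Day 22+7 gives 22 − 1 = 21 to 21 + 7 = 28. SAP 4.4.5 states the same for the dose 2 visit: "protocol defined window of 21-28 days post first vaccination".

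**Reproducing the SAP limits.** SAP 6.3.3 drops data more than one day out of window, so PP limits = visit window widened by one day on each side.

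| Visit | Window (days after dose) | Widened by 1 | SAP 6.3.3 |
|---|---|---|---|
| 3 (Day 8+2) | 7–9 | 6–10 | 6–10 |
| 4 (Day 22+7) | 21–28 | 20–29 | 20–29 |
| 6 (Day 8+2, from 8.2.5) | 7–9 | 6–10 | 6–10 |
| 7 (Day 22+7) | 21–28 | 20–29 | 20–29 |
| 10 (Day 181±14) | 166–194 | 165–195 | 165–195 |
| 6 (D8±3d, from Table 2) | 4–10 | 3–11 | 6–10, no match |

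Reading Table 2 as +3 only gives 7–10, widened to 6–11, which also fails to match.

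**Early-termination serum against Visit 07.**
- The rule covers days up to and including 21.
- Visit window 21–28 (8 days): day 21 is covered and days 22–28 are not, so 7 of 8 are uncovered.
- SAP PP window 20–29 (10 days): days 20 and 21 are covered and days 22–29 are not, so 8 of 10 are uncovered.
- Visit 10 window 166–194 (194 − 166 + 1 = 29 days): none is covered. This time point is exploratory.

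**Early-termination safety labs and diary review against Visits 03/06.** The limit is 7 days and the visit window is 7–9, so days 8 and 9 are outside the limit. Antibody serum is still collected on those days, because 8 and 9 are below 21.

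**Unscheduled visits.** Section 8.2.12 words the serum limit to include day 21. The unscheduled column of Appendix A requires the visit to come before day 21, which leaves no overlap with the Visit 07 window.

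**Visit 06 under Table 2.** Days 4–10 are permitted and the SAP keeps 6–10, so days 4 and 5 are permitted by Table 2 and dropped from PP.

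**After alignment.** If serum is collected through day 28, all 8 Visit 07 days are covered. If Table 2 and Section 8.2.5 gave the same D8+2d window, no permitted Visit 06 day would be dropped from PP.

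**The case against.** The best reply is that 8.2.11 lists what is done at a termination visit and does not forbid a scheduled visit that is due. A subject in clinic on days 22 to 28 is inside the Visit 07 window, and Visit 07 collects serum without condition. A site could run the contact as Visit 07. This stands as a reason why the loss is not certain. It does not remove the conflict, because 8.2.11 does not tell the site to do so and its stated limit points the other way.

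The 7-day limits on labs and diary can also be defended. They follow the endpoint definitions, which run to 7 days (approximately 7 for labs), and a phone review of the diary takes place around Day 4 after each dose. That part is a matter of reconciliation only.

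On Visit 06, Table 2 is the odd one out, and the SAP limits agree with 8.2.5. Under the visit text a draw on day 4 or 5 is already out of window, so the SAP is consistent in dropping it. The Table 2 header is also partly garbled in the machine-read text, so the ±3 should be confirmed on the printed page. All of this stands. What remains is that the table sites would consult for blood draws gives a different window.

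**Conclusion.** Both conflicts are present in the text, and both are small. Only one route leads to a lost primary sample: termination on days 22 to 28 after dose 2, with Visit 07 not done and the contact not run as Visit 07. The documents give no count for this. The 5% and 12% in Protocol 11.4.2 cover every reason for PP exclusion and cannot be used as a rate for it. Margins are thinnest in the unadjuvanted arms aged 65 and over: 30 × (1 − 0.12) = 26.4 expected against a target of 25, if enrollment stops at its minimum.

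A reader might infer that every termination inside any of these windows loses a primary result. The documents do not support that. On days 8 and 9 serum is still drawn, and the Day 202 titers are exploratory. A reader might also infer that the Table 2 conflict threatens the primary immunogenicity endpoint. It does not: it touches a secondary titer time point (Day 29) and the timing of the post-dose-2 safety labs.

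The conclusion rests on counting vaccination day as Day 1, which the SAP confirms, and on Table 2 having been read correctly.

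**What to change.** 1. In Protocol 8.2.11, Appendix A and SAP Table 3, state that antibody serum is collected at early termination whenever the visit falls inside a scheduled immunogenicity window and that sample has not been drawn. For Day 43 this means through 28 days after dose 2. The same wording would cover the Day 202 window.
2. Reconcile the 7-day limits for early-termination safety labs and diary review with the 7 to 9 day window of Visits 03 and 06, and reconcile the unscheduled-visit wording in 8.2.12 with Appendix A.
3. Reconcile the Visit 06 window in protocol Table 2 with Section 8.2.5, Appendix A, SAP Table 2 and SAP 6.3.3, so that no draw permitted by one passage is excluded by another.

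The cost is wording changes in the protocol and one SAP table, and at most one extra 10 mL draw in a few terminating subjects who are already in clinic. Sample size and analysis methods are unchanged.

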8.2.12 Unscheduled Visit (if needed)

Unscheduled visits may occur at any time during this trial. Any of the following activities may be performed:

- Interim medical history, including an assessment for new medical conditions and symptoms suggestive of PIMMCs, will be obtained by interview of subjects and any changes since the previous clinic visit or contact will be noted (if indicated).
- Memory aid information will be reviewed with subjects (if within 7 days after the last study vaccination).
- All concomitant medications will be recorded on the appropriate data collection form (if within 21 days after the last study vaccination). Receipt of any non-study influenza vaccine, including those that are experimental, what type (inactivated or live attenuated), what subtype (e.g., A/H3, A/H5, A/H9) and approximate date of vaccination will be recorded on the appropriate DCF, if known and not previously collected will be recorded if within 180 days after the second study vaccination.

- All AE/SAEs will be recorded on the appropriate data collection form. AEs will be limited to SAEs, MAAEs, including NOCMCs, and PIMMCs if after 21 days after the last study vaccination.
- Vital signs, including oral temperature, pulse, and blood pressure, may be obtained if indicated. Subjects must not eat or drink anything hot or cold, or smoke within 10 minutes prior to taking oral temperature.
- A targeted physical examination, including an assessment for signs suggestive of PIMMCs, may be performed, if indicated based on review of interim medical history, by a study clinician licensed to make medical diagnoses and listed on the Form FDA 1572 as the site principal investigator or sub-investigator.
- The study vaccination site will be examined (if within 7 days after the last study vaccination).
- Post-administration reactogenicity assessments will be performed (if within 7 days after the last study vaccination).
- Approximately 10 mL of venous blood will be collected for WBC, Hgb, PLT, ALT, T. Bili, Cr, and performed by the central (clinical) laboratory (if indicated).
- Approximately 10 mL of venous blood will be collected for serum antibody assays (if within 21 days after the last study vaccination).
- Approximately 10 mL of venous blood will be collected for future research from subjects who consent to collection of serum for future use (if within 21 days after the last study vaccination), either by signing an informed consent form that includes collection of future use samples as a condition of study participation or by indicating that they opt in to sample collection for future use if the informed consent form allows the option to choose that option.

9 ASSESSMENT OF SAFETY

9.1 Specification of Safety Parameters

Safety will be assessed by the frequency and severity of:

- 1. SAEs occurring from the time of the first study vaccination through approximately 12 months after the last study vaccination.
- 2. Solicited AEs reactogenicity events occurring from the time of each study vaccination through 7 days after each study vaccination:
 - a) Injection site reactions including pruritus, ecchymosis, erythema, induration/swelling, pain, and tenderness.
 - b) Systemic reactions including fever, feverishness, fatigue, malaise, myalgia, arthralgia, headache, and nausea.
- 3. Clinical safety laboratory AEs occurring from the time of each study vaccination through approximately 7 days after each study vaccination. Parameters to be evaluated include WBC, Hgb, PLT, ALT, T. Bili, Cr.
- 4. Unsolicited AEs –non-serious AEs occurring from the time of each study vaccination through approximately 21 days after each study vaccination.
- 5. MAAEs, including NOCMCs, and PIMMCs occurring from the time of the first study vaccination through approximately 12 months after the last study vaccination.

9.2 Methods and Timing for Assessing, Recording, and Analyzing Safety Parameters

9.2.1 Adverse Events

Adverse Event (AE): (ICH) E6 defines an AE as any untoward medical occurrence in a patient or clinical investigation subject administered a pharmaceutical product regardless of its causal relationship to the study treatment. An AE can therefore be any unfavorable and unintended sign (including an abnormal laboratory finding), symptom, or disease temporally associated with the use of a medicinal (investigational) product. The occurrence of an AE may come to the attention of study personnel during study visits and interviews of a study recipient presenting for medical care, or upon review by a study monitor.

AEs, including solicited injection site and systemic (subjective and quantitative) reactions, not meeting the protocol-defined criteria for SAEs will be captured on the appropriate data collection form and eCRF. Information to be collected for unsolicited non-serious AEs includes event description, date of onset, licensed study clinician's assessment of severity and relationship to study product and alternate etiology (if not related to study product) (assessed only by those with the training and authority to make a diagnosis and listed on the Form FDA 1572 as the site principal investigator or sub-investigator), date of resolution of the event, seriousness, and outcome. AEs occurring during the trial collection and reporting period will be documented appropriately regardless of relationship. AEs will be followed through resolution.

Any medical condition that is present at the time that the subject is screened will be considered as baseline and not reported as an AE. However, if the severity of any pre-existing medical condition increases, it will be recorded as an AE.

AEs must be graded for severity and assessed for relationship to study product (see definitions below). AEs characterized as intermittent require documentation of onset and duration of each episode. The start and stop date of each reported AE will be recorded on the appropriate data collection form and eCRF.

FDA defines an AE as any untoward medical occurrence associated with the use of a drug in humans, whether or not considered drug related.

New-Onset Chronic Medical Conditions (NOCMCs): NOCMCs are defined as any new ICD-10 diagnosis that is applied to the subject during the duration of the study, after receipt of the study agent, that is expected to continue for at least 3 months and requires continued health care intervention.

Medically-Attended Adverse Events (MAAEs): For each unsolicited AE experienced, the subject will be asked if he/she had received medical attention, defined as hospitalization, an emergency room visit, or an otherwise unscheduled visit to or from medical personnel for any reason. AEs characterized by such unscheduled medical care will be designated as MAAEs.

Potentially Immune-Mediated Medical Conditions (PIMMCs): PIMMCs constitute a group of AEs that includes diseases which are clearly autoimmune in etiology and other inflammatory and/or neurologic disorders which may or may not have autoimmune etiologies. PIMMCs currently in effect are presented in Appendix B: List of PIMMCs.

Severity of Event: AEs will be assessed by a licensed study clinician listed on the Form FDA 1572 as the site principal investigator or appropriate sub-investigator using a protocol-defined grading system (see Sections 9.2.2 and 9.2.3). For events not included in the protocol-defined grading system, the following guidelines will be used to quantify severity:

- Mild (Grade 1): Events require minimal or no treatment and do not interfere with the subject's daily activities.
- Moderate (Grade 2): Events result in a low level of inconvenience or concern with therapeutic measures. Moderate events may cause some interference with functioning and daily activities.
- Severe (Grade 3): Events interrupt the subject's daily activities and may require systemic drug therapy or other treatment. Severe events are usually incapacitating.

Relationship to Study Product: The licensed study clinician's assessment of an AE's relationship to study product is part of the documentation process, but it is not a factor in determining what is or is not reported in this trial. If there is any doubt as to whether a clinical observation is an AE, the event should be reported. The relationship to study product must be assessed for AEs using the terms: related or not related. In a clinical trial, the study product must always be suspect. To help assess, the following guidelines are used:

- Related There is a reasonable possibility that the study product caused the AE. Reasonable possibility means that there is evidence to suggest a causal relationship between the study product and the AE.
- Not Related There is not a reasonable possibility that the administration of the study product caused the event.

